C) Facilitator Experience (professional vs community). We hypothesise that although professional facilitators may achieve higher levels of implementation, community facilitators may be a more cost-effective approach and may also result in better implementation due to stronger buy-in at the community level. As a result, there will be no difference between components on VAWC (via indirect effects).

8. Trial design

We will use an effectiveness-implementation hybrid type 2 design to a) determine the effectiveness and cost-effectiveness of PfR, and b) determine the feasibility and impact of three different implementation strategies in terms of programme delivery.[21] We will conduct a cluster randomised controlled trial (cRCT) in a total of 54 clusters (1:1 intervention: control; 4 groups of 10 parents per cluster, 50% male 50% female, 2,160 in total or 1,080 adult participants per arm). In addition, approximately 1,080 children 10-14 years will be assessed ($N = 540$ per arm). We will also assess the quality of delivery of PfR in terms of competent adherence of 108 facilitators (1 per group, 4 per cluster).

We will also examine three different factors related to programme implementation within the clusters allocated to PfR (approximately 27 clusters, 40 parents per cluster): 1) geographical location (rural vs. peri-urban), 2) group composition (existing vs. newly formed groups), and 3) facilitator experience (experience vs. novice). Efforts will be made to have equal numbers of clusters receiving each type of component by testing every combination of implementation components in eight different experimental conditions ($N 3$ clusters and 120 families per condition).

Section 3: Methods

9. Study setting

The study will be conducted in two districts, Wakiso and Amuru, each of them contributing parental participants to both intervention and control arms. Participating clusters will either be villages or wards (i.e., groups of villages) depending on their population size and geographical proximity.

10. Eligibility criteria

Participants must have provided written, informed consent prior to the occurrence of any study procedures.

Inclusion criteria for participating parents or caregivers:

1. Age 18 or older;
2. Primary caregiver responsible for the care of a child between the ages of 10 and 14;
3. Agreement to participate in the PfR programme if allocated to the treatment condition;
4. Provision of consent to participate in the full study.

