Time cost for delivery – Facilitator Report

Time cost for delivery will be collected from facilitator weekly reports and based on the time spent on training, preparation, travel to and from, and delivery of each session/lecture. The total time will be summed for each facilitator and then mean scores will be created for the sample.

[Time Frame: 8-months post-baseline]

Implementation fidelity – Facilitator Report

Implementation fidelity by programme facilitators of the PfR programme will be examined using self-report checklists by the programme facilitators. They will report on 5 items per session/lecture ranging from an impression of the quality of delivery to the proportion of the session activities they were able to deliver (0 = No time for it to 5 = all of the activities).

[Time Frame: 8-months post-baseline]

Competent adherence – Observational

Competent adherence will be assessed using the PfR Facilitator Assessment Tool (PfR-FAT) [39]. The PfR-FAT was developed by the study investigators and programme developers to assess the proficiency of programme delivery by facilitators as a prerequisite to certification. Three standard behaviour categories are based on the core process skills (25 items), includes modelling skills (6 items, e.g., “give positive, specific, and realistic instructions”), collaborative facilitation (7 items, e.g., “accept participant responses verbally by reflecting back what the participant says”), and group management and leadership

skills (12 items, e.g., “use open-ended questions during group discussions”). Items are summed to create a total score of competent adherence.

[Time Frame: 8-months post-baseline]

Qualitative outcomes

Qualitative data will be collected using live observation of programme delivery (at least 1 observation per group, N=32); in-depth interviews with senior implementation staff (N=4), trainers of facilitators (N=2) and a sample of facilitators (N=16); focus group discussions with caregivers (N=8, 10 per FGD). In addition, data will be collected through semi-structured interviews with Wakiso and A District Community Development Services (N=4) who will provide supervision of the NGO implementing partner (SOS) and from a sample of local community leaders (N=8), each lasting from 60 – 90 minutes.

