We will investigate programme implementation and participation of PfR and its association to primary outcomes. First, quantitative data will be examined to determine whether the programme was implemented to an acceptable degree of fidelity, exposure, adherence, engagement, and participant satisfaction. Secondly, although limited by sample size, multivariate regression analyses will explore potential associations between programme feasibility outcomes and change scores for child maltreatment and partner conflict outcomes. Finally, analysis of qualitative data from participant focus groups and facilitator interviews will provide more nuanced information on programme feasibility. Using a grounded theory approach similar to that used in the development phase, this study will explore cultural acceptability and appropriateness, barriers to implementation and participation, and potential approaches to overcoming these barriers.

Programme implementation – quantitative data analysis

Implementation fidelity will be analysed by examining data from the facilitator self-report checklists and the PfR Facilitator Assessment Tool [39]. First, internal consistency with means and standard deviation per group for each measurement will be reported. Next, differences between methodological approaches in overall fidelity scores will be assessed with independent t-tests. This will help determine the reliability and consistency of using self-report versus observational assessments of fidelity. Then, in order to produce a basic level of fidelity, a ratio of program implementation to program design will be created for both self-report and observational scores [55]. According to Borrelli and colleagues, a standard of 80% programme fidelity will be considered as “high treatment fidelity” [56]. In addition, this study will examine challenges in facilitating specific components or aspects of delivery quality. For instance, facilitators may have difficulty implementing a particular session activity or have difficulty practicing reflexive behaviour with participants. Combined with in-depth interviews on barriers to implementation, this may highlight the need for additional training and/or further adaptation of programme materials.

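### Self-reported and observed fidelity are matched scores, yet the protocol compares them with independent t-tests, and no test of means can show the reliability it is after

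*Protocol*

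**What the plan says.** Protocol section 20, under the quantitative analysis of programme implementation, bases the fidelity analysis on "data from the facilitator self-report checklists and the PfR Facilitator Assessment Tool" (PfR-FAT). It first reports internal consistency, means and SDs for each measure. It then says that "differences between methodological approaches in overall fidelity scores will be assessed with independent t-tests", and gives the reason: "This will help determine the reliability and consistency of using self-report versus observational assessments of fidelity". Only after that does it form a ratio of implementation to programme design for each kind of score and state an 80% standard for high fidelity.

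Section 15, under Process outcomes, describes the two tools:

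- Implementation fidelity "will be examined using self-report checklists by the programme facilitators". On the content: "They will report on 5 items per session/lecture ranging from an impression of the quality of delivery to the proportion of the session activities" that could be delivered, with 0 to 5 given as the scoring for that last item.
- Competent adherence uses the PfR-FAT, an observational tool "to assess the proficiency of programme delivery by facilitators as a prerequisite to certification". On its content: "Three standard behaviour categories are based on the core process skills (25 items" in all), summed to a total.

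Section 8 plans to assess "competent adherence of 108 facilitators (1 per group, 4 per cluster").

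**The concern.** There are three difficulties.

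1. **Matching.** The facilitators who complete the checklist are also the people observed with the PfR-FAT. A facilitator or group with both scores contributes a pair. An independent-samples test treats the two scores as coming from unrelated people, so its standard error is wrong unless the scores are uncorrelated.
2. **Purpose.** Reliability and consistency between methods concern whether the two scores move together and lie close for the same facilitator. A comparison of means addresses neither. Two unrelated measures with equal means would look consistent, and two almost perfectly correlated measures with a constant offset would look inconsistent. Making the test paired cures the first difficulty but not this one.
3. **Scale.** A per-session checklist of 5 items and a sum of 25 skill items are not in the same units, so a raw mean difference need not reflect a difference in fidelity.

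At stake is what the process evaluation can say about facilitator self-report as a measure of fidelity. Programme fidelity and quality of delivery are outcomes under Objective 3 and enter the complier average causal effect analysis, so a sound check on the measures is worth having.

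**Working it through.** The protocol gives no sample size, power or error rate for this comparison, so there is no stated figure to reproduce. The one related count checks: 27 PfR clusters × 4 groups × 1 facilitator = 108.

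**Inputs**

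- Number of pairs: n = 108 (section 8), if every assessed facilitator also has a checklist score.
- Significance level: two-sided 5%. This is an assumption; it is the level section 20 sets for outcome tests, and none is given for this test.
- Correlation r between the two scores for the same facilitator: not stated. Assumed range -0.3 to 0.7.
- Equal SDs and a common scale: assumed.

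**Step 1: size of the independent test on matched data.** The test uses SE = SD × √(2/n), but the true SE of the mean difference is SD × √(2(1−r)/n). In large samples the true size is therefore 2 × (1 − Φ(1.96/√(1−r))).

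| r | 1.96/√(1−r) | True size at nominal 5% | Simulated, n = 108 |
|---|---|---|---|
| -0.3 | 1.72 | 8.6% | 8.6% |
| 0 | 1.96 | 5.0% | 5.1% |
| 0.3 | 2.34 | 1.9% | 2.0% |
| 0.5 | 2.77 | 0.6% | 0.6% |
| 0.7 | 3.58 | 0.03% | 0.03% |

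The simulation used 20,000 replicates of bivariate normal data. The paired test stayed close to 5% throughout.

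**Step 2: power for a 0.3 SD mean difference, n = 108 (same simulation).**

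| r | Independent test | Paired test |
|---|---|---|
| 0.3 | 61% | 75% |
| 0.5 | 62% | 87% |
| 0.7 | 67% | 98% |

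The observed difference needed for significance is 1/√(1−r) times that of the paired test, or about 1.2, 1.4 and 1.8. The true difference detectable with 80% power rises by less: (1.96/√(1−r) + 0.84)/2.80, or about 1.14, 1.29 and 1.58.

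**Step 3: can the test show agreement?** Lin's concordance coefficient with equal SDs and a mean shift of d SDs is 2r/(2 + d²).

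- r = 0, d = 0: concordance is 0, so there is no agreement. The test is non-significant in about 95% of replicates.
- r = 0.95, d = 0.5: concordance is 1.9/2.25 = 0.84. The test is significant in about 100% of replicates.

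If significance is taken as a sign of inconsistency, the answer is wrong in both cases. This step does not depend on the true correlation.

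**Step 4: scale.** Assume all 5 checklist items run 0 to 5, giving a session maximum of 5 × 5 = 25. The PfR-FAT item range is not stated; an item maximum of 1 to 5 gives a total maximum of 25 to 125. At 80% fidelity on both, the raw means would be 20 against 20 to 100. A large raw difference can therefore arise with identical fidelity.

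**The case against.** Several points on the other side stand.

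- **Pairing is inferred.** No single sentence says both tools are applied to the same facilitators; it follows from sections 8, 15 and 20 together. Section 8 counts one facilitator per group while section 14 has two delivering the programme, and how session checklists become an overall score is not stated. Overlap may be partial, but any matched subset is still paired.
- **The size distortion depends on r.** At r = 0 the test has the right size, and at r = -0.3 it rejects too often. If the tools capture different things, r near 0 is plausible. The loss of size and power is therefore conditional; the failure to measure agreement is not.
- **The tools differ in content.** The checklist covers activities delivered plus an impression of quality, while the PfR-FAT covers process skills. Expressing both as percentages gives common units, not a common construct, so limits of agreement and an intraclass correlation could also mislead if applied to everything.

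A reader might infer more than the protocol supports:

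- That this test decides whether self-report can replace observation. The protocol says only that it will help in judging the two methods. The ratios are formed for both scores whatever the test shows, and nothing makes the 80% standard, the mixed models or the complier analysis depend on the result.
- That over-reporting by facilitators will go undetected. On the assumed figures power falls; it does not vanish.
- That the protocol will read a non-significant result as consistency. It does not say so, though the stated purpose invites that reading.

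**Conclusion.** The point holds. The named test does not fit its stated purpose, and this is not something left open for an analysis plan, because the protocol fixes both the test and the reason for it. The failure to show reliability or agreement rests on no assumed value. The mismatch with paired data holds wherever both scores exist for a facilitator or group. Its numerical effect rests on assumed correlations, equal SDs, a 5% level and full coverage of 108 facilitators: a true size anywhere from about 8.6% to 0.03%, and a power loss of roughly 14 to 31 percentage points at r = 0.3 to 0.7 (75 − 61 = 14; 98 − 67 = 31).

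The consequence is confined to a conclusion of the process evaluation. The primary effectiveness analysis is unaffected. It should be corrected, but it is not a threat to the trial.

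**What to change.** Amend the paragraph in section 20 as follows:

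1. Form the percentage-of-design ratios first, for both self-report and observed scores, and say how session checklists are aggregated.
2. Match the scores by facilitator or group and report how many have both.
3. Replace the independent t-test with the between-method correlation and the paired mean difference with its confidence interval, allowing for cluster.
4. Add limits of agreement and an intraclass correlation only where the rescaled scores cover comparable content.
5. State that a non-significant difference will not be read as consistency.

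The cost is a short wording change and minor analysis code, with no new data. Section 27 requires formal amendment for changes to analyses, agreed by the Trials Steering Committee and approved by the ethics committees, so this is best bundled with any other amendment.

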Data collected from the process evaluation will investigate the implementation of the PfR programme. Quantitative data will be collected to examine implementation fidelity, competent adherence, and participation. Qualitative data will also examine barriers to implementation and participation, and potential approaches to overcoming these barriers.

Recruitment rate – Assessor Report

Recruitment rate will be based on the number of families who were eligible for inclusion and provided consent to participate in the program divided by the number of target population who were exposed to recruitment activities.

[Time Frame: 8-months post-baseline]

Enrolment rate – Facilitator Report

Enrolment rate will be based on the number of families who attend either at least one session of *Parenting for Respectability* or the *Parenting in a Nutshell* lecture divided by the number of families allocated to either study arm. Separate enrolment rates will be assessed for each arm

[Time Frame: 8-months post-baseline]

Participation rate – Parenting for Respectability participants only – Facilitator Report

Participation rates for those allocated to the PfR programme will be mean attendance rate for programme sessions based on those families who enrolled in the programme (i.e., parents who attended at least one session). We will also assess the percentage of families who enrolled in the programme who attended 50% (e.g., 8 sessions) and 75% (e.g., 12 sessions) or more.

[Time Frame: 8-months post-baseline]

Dropout rate – Facilitator Report

Dropout rates for enrolled participants will be defined as the percentage of participants who fail to attend at least three consecutive sessions and do not attend any sessions at a later stage.

[Time Frame: 8-months post-baseline]

Completion rate – Facilitator Report

Completion rates for participants will be determined based on the number of enrolled participants who attend a cut-off threshold of at least 62.5% of the programme (i.e., 10 sessions) [38].

[Time Frame: 8-months post-baseline]

Implementation dosage (time) – Facilitator Report

Implementation dosage will be based on the total amount of time in minutes that the program was delivered to each parent. Facilitators will report on the start and end time of each session/lecture in their weekly reports. Implementation dosage will be based on the total amount of time delivered divided by the mean attendance rate.

[Time Frame: 8-months post-baseline]

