Data collectors who are fluent in Luganda for Wakiso and Acholi for Amuru and who have prior experience working with vulnerable families in Uganda will serve as research assistants. They will be extensively trained in ethics, informed consent, interviewing, and observational assessment techniques by the study investigators. All data collection points will have a detailed protocol and will be scripted to ensure consistency across data collectors. Research assistants will be managed by the project coordinator ([name]) and supervised by PI [name]. Quantitative self-report assessments and qualitative interview/focus group guides will be translated into Luganda and Acholi by bilingual researchers and the translation checked by back-translation [42].

The proposed study will use an innovative, low-cost technological data collection tool using Computer-Assisted Self-Interviewing ('CASI') methods with e-tablet technology to administer consent forms and questionnaires. This method of data collection has been pilot-tested during the previous feasibility study with high acceptability to respondents. Trained data collectors will explain the CASI procedures, read out questions, and assist participants to key in responses to their handsets. CASI supports multiple languages, and so can include English, Luganda, and Acholi. If any participants are unable or uncomfortable with the use of tablets, a paper-and-pen interviewer-assisted questionnaire will also be available in English, Luganda, and Acholi.

Data on implementation fidelity will be collected live at all programme sessions. Programme adherence data will be collected using attendance registers administered by research assistants assigned to the process evaluation. Programme participants will indicate whether they completed their home activity assignments using self-report checklists.

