Overall programme exposure, adherence, and engagement will be assessed based on attendance registers. Mean scores and standard deviations will be reported on attendance rates, completion rates, and activity engagement. In the previous delivery of the PfR, it has been recommended that parents participate in at

least 50% or 8 sessions. As a result, a similar standard will be used to determine an acceptable overall rate of programme attendance. This study will also report percentages of parents who participate in 50%, 25%, and 10% of the programme.

Finally, we will use the Complier Average Causal Effect analyses that provides an estimate of intervention effects, taking into account implementation (i.e., compliance) and other baseline predictors of attendance [57, 58]. These include implementation fidelity (competent adherence and content delivery) and attendance rates. This data will provide useful information on whether programme fidelity and acceptability have a role in influencing programme effects. This will be particularly useful for improving the intervention protocols and training prior to further implementation and evaluation [59].

Programme implementation – qualitative data analysis

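### The complier (CACE) paragraph mixes facilitator fidelity with participant compliance and with baseline predictors; if fidelity helps define compliers, the estimate may be biased, probably away from the null

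*Protocol*

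**What the plan says.** The last paragraph of Protocol Section 20, Programme implementation – quantitative data analysis, introduces the CACE analysis as one "taking into account implementation (i.e., compliance) and other baseline predictors of attendance". The next sentence reads: "These include implementation fidelity (competent adherence and content delivery) and attendance rates". Its stated purpose is: "This data will provide useful information on whether programme fidelity and acceptability have a role in influencing programme effects".

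Other sections show what fidelity is:
- Section 15, Implementation fidelity: "Implementation fidelity by programme facilitators of the PfR programme will be examined using self-report checklists by the programme facilitators".
- Section 15, Competent adherence: the PfR Facilitator Assessment Tool (PfR-FAT) is used to "assess the proficiency of programme delivery by facilitators as a prerequisite to certification".
- Section 18, Data collection: "Data on implementation fidelity will be collected live at all programme sessions".

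For attendance, Section 20 recalls an earlier recommendation of at least 50%, or 8 sessions, and says that "a similar standard will be used to determine an acceptable overall rate of programme attendance". This standard is not linked to the CACE analysis. Nor is the 80% level that the same section uses for high fidelity. The effectiveness analyses in Section 20 are by intention to treat.

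**The concern.** A complier analysis classifies each participant by whether he or she would take up the allocated programme. It assumes that allocation has no effect on the outcome in those who would not (the exclusion restriction). Covariates that predict compliance must be known before randomisation and in both arms.

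Facilitator fidelity fits neither role. It belongs to the facilitator and the group, not to the parent, and it comes into being during delivery. A parent who attends a poorly delivered PfR group still attends PfR. If that parent is classed as a non-complier, whatever he or she gains is attributed to the parents who remain compliers.

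At stake is a supplementary estimate meant to guide programme protocols and training. Whether fidelity changes the effect is a dose or moderator question, which a complier analysis does not answer.

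**Working it through.** **Reading the text.** The word that opens the second sentence has no clear antecedent, so there are two readings.

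1. It refers to implementation, which the first sentence equates with compliance. Fidelity then forms part of compliance. Section 15 shows that both fidelity measures describe facilitators' delivery, so this is not participant uptake.
2. It refers to the baseline predictors. Fidelity and attendance then act as baseline covariates. Section 18 has fidelity collected at the sessions, and attendance also occurs at the sessions. Section 12 places randomisation immediately after baseline data collection, so neither is a baseline variable.

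Both readings are faulty. Only the first leads to a calculable bias.

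**Plan's own figure.** There is none. The protocol gives no complier share, complier threshold or complier effect.

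**Inputs.** From the protocol: 54 clusters allocated 1:1 (27 per arm), four groups of 10 parents per cluster (Section 8), ICC 0.05 (Section 13). Assumed:
- a = share of parents who attend;
- f = share in high-fidelity groups, independent of attendance;
- D = effect in attenders of high-fidelity groups;
- r = fraction of D gained by attenders of low-fidelity groups.

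Parents who do not attend are taken to gain nothing, and effects are mean differences.

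**Formula.** The intention-to-treat effect is

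ITT = a·D·[f + (1 − f)·r].

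If a complier must attend and be in a high-fidelity group, the complier share is a·f. The instrumental-variable (Wald) estimate is then

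ITT/(a·f) = D·[f + (1 − f)·r]/f = D·[1 + r(1 − f)/f].

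The attendance share a cancels.

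| f | r = 0 | r = 0.25 | r = 0.5 | r = 1 |
|---|---|---|---|---|
| 0.8 | 1.00 | 1.06 | 1.13 | 1.25 |
| 0.7 | 1.00 | 1.11 | 1.21 | 1.43 |
| 0.5 | 1.00 | 1.25 | 1.50 | 2.00 |

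For example, at f = 0.5 and r = 0.5: 1 + 0.5 × 0.5/0.5 = 1.50.

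**Simulation check.** The trial's cluster and group structure was simulated with fidelity drawn per group, a = f = 0.7 and D = −0.30 SD (1,500 trials per setting).

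| r | Complier = attends and high fidelity (target −0.30) | Complier = attends | True mean effect in attenders, D·[f + (1 − f)·r] |
|---|---|---|---|
| 0 | −0.293 | −0.205 | −0.210 |
| 0.25 | −0.334 | −0.233 | −0.233 |
| 0.5 | −0.366 | −0.256 | −0.255 |
| 1 | −0.427 | −0.298 | −0.300 |

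The first estimate follows the formula: at r = 1, −0.30 × 1.43 = −0.429. The attendance-only estimate recovers the mean effect among attenders at the fidelity actually delivered.

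**Limit of the attendance-only version.** It is unbiased here because parents below the cut-off are assumed to gain nothing. Suppose a share c reaches the cut-off, and a further share s attends below it and gains a fraction g of the effect. The inflation is then (c + s·g)/c. For c = 0.5 to 0.7, s = 0.1 to 0.3 and g = 0.25 to 0.5, it runs from 1.04 (0.7, 0.1, 0.25) to 1.30 (0.5, 0.3, 0.5).

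**The case against.** The protocol never defines a complier, never says that fidelity enters a complier cut-off and names no estimator. Threshold and estimator are commonly left to the SAP. CACE appears once, at the end of the quantitative process evaluation, and no hypothesis or power calculation rests on it. A separate analysis of implementation against outcome is already planned (Objective 4 in Section 7; Implementation outcome analyses in Section 20).

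Most of this stands. It limits the point to one supplementary analysis and makes the bias conditional. It does not rescue the paragraph, because the protocol does state that fidelity is an input, and neither role open to it is valid.

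Three stronger inferences are tempting and should not be drawn:

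- *That the analysis will overstate the effect.* This needs fidelity inside the complier definition and some benefit in low-fidelity groups. With r = 0 there is no inflation. If poor delivery did harm (r < 0), the estimate would be too small.
- *That the protocol carries rival complier cut-offs that could be used to tune the result.* In Section 15, 50% and 75% are descriptive participation levels and 62.5% (10 sessions) defines completion. None is tied to CACE.
- *That fidelity fails as compliance because the PfR-FAT applies only to PfR.* With access to PfR in one arm only, compliance is normally observed only in that arm, and PfR attendance has the same feature. The need for values in both arms applies to covariates.

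**Conclusion.** The point holds in conditional form. The CACE paragraph combines a group-level measure of delivery, taken after randomisation, with participant compliance and with baseline predictors. If fidelity helps define compliers, the exclusion restriction is doubtful and the estimate may be biased, probably away from the null. The inflation would be about 1.06 to 1.25 if 80% of parents are in high-fidelity groups and 1.25 to 2.00 if 50% are, for r between 0.25 and 1.

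These figures rest on assumed shares, on no benefit in non-attenders and on effects expressed as mean differences. They were not worked out on the rate-ratio scale that Section 20 plans for skewed outcomes. If fidelity or attendance is instead a baseline predictor, the fault is one of timing, and no size is attached to it. The intention-to-treat results do not depend on any of this.

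**What to change.** Rewrite the CACE paragraph in Section 20 so that:

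1. compliance is defined by the parent's own attendance and nothing else;
2. predictors of compliance are limited to covariates measured at baseline in both arms;
3. fidelity (checklists and PfR-FAT) is examined in the within-PfR association analysis already planned under Implementation outcome analyses, and reported as a non-randomised association.

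The attendance threshold can be set in the SAP. A definition of at least one session should be reported alongside the 8-session standard, because any higher cut-off is also inflated if parents below it benefit. The choice is a trade-off: one session protects the exclusion restriction but counts barely exposed parents as compliers.

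No new data are needed, since attendance registers are already planned. The cost is SAP wording and a short protocol amendment, because Section 27 requires one for changes to analyses. It is best made before outcome data are seen. The price is probably a smaller complier estimate, and the fidelity question will be answered only by association.
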